## Research Summary

**1. Protocol Title:** Non-Invasive Diagnosis of Pulmonary Vascular Disease Using Inhaled  $^{129}\text{Xe}$  Magnetic Resonance Imaging

**2. Purpose of the Study:** To develop a novel, non-invasive means of comprehensively diagnosing and monitoring response to therapy in PVD using MR imaging (MRI). Our approach uses hyperpolarized  $^{129}\text{Xenon}$  ( $^{129}\text{Xe}$ )-MRI, a novel technology that images lung ventilation, microstructure, and gas exchange.

**3. Background & Significance:**

Pulmonary arterial hypertension (PAH) carries a significant economic burden, with average annual health care costs of ~ \$100,000/yr. The diagnosis of PAH can be challenging, as it requires fulfillment of specific clinical and hemodynamic criteria. However, these are limited because they do not allow the diagnosis of PAH in the setting of concomitant left heart disease or lung disease. For example, patients with *mild to moderate* left heart disease or chronic obstructive pulmonary disease, which are common in older patients, technically cannot be diagnosed with PAH because *severe* left heart and lung disease can cause PH. Similarly, hemodynamic criteria are limited by arbitrary cutoffs for mean pulmonary artery pressure (mPAP), pulmonary capillary wedge pressure (PCWP), and pulmonary vascular resistance (PVR) obtained at right heart catheterization (RHC) (PH is defined as mPAP  $\geq$  25 mmHg; PAH is defined as mPAP  $\geq$  25-mmHg *and* a PCWP  $\leq$  15 mmHg, with some criteria recommending an additional cutoff of PVR  $\geq$  3 Woods units. Moreover, it is currently unclear what constitutes abnormal hemodynamics in the setting of concomitant heart disease, which can increase the filling pressures of the heart (the PCWP), or in lung disease, which can increase the PVR. These hemodynamic criteria also frequently exclude patients who may have a borderline elevation in mPAP or abnormalities primarily associated with exercise that are not captured with a resting heart catheterization. As the majority of patients who are now evaluated for PAH are older with common cardiac and pulmonary comorbidities, the clinical and hemodynamic criteria are frequently inadequate for diagnosing patients who actually have PVD.

This work seeks to apply and test a novel non-invasive methodology, hyperpolarized (HP)  $^{129}\text{Xenon}$  (Xe) magnetic resonance imaging (MRI), for the diagnosis of PVD. Hyperpolarized  $^{129}\text{Xe}$  MRI has been under active development and used in clinical research at Duke for over 7 years. It has been used in 5 IRB protocols, 3 of which are currently active. Over 250 patients and volunteers have undergone  $^{129}\text{Xe}$  MRI. The technology permits 3D quantitative imaging of both pulmonary ventilation and gas exchange during a breath-hold exam. It has been used at Duke and around the world to study COPD, asthma, and interstitial lung disease. However, until recently it has not been applied to PVD. In preliminary studies under an existing protocol, two patients in whom PVD was suspected, but who did not meet strict PAH criteria, underwent  $^{129}\text{Xe}$ -MRI research studies. These patients had no other evidence of significant lung disease, despite undergoing a thorough evaluation that included pulmonary function tests, CT scan, and RHC. In both patients, the  $^{129}\text{Xe}$  study demonstrated spectroscopic and imaging indices consistent with a barrier to diffusion of  $^{129}\text{Xe}$  to red blood cells (RBCs). These patients subsequently had lung tissue obtained (one at time of lung transplant, the other with a surgical lung biopsy). Strikingly, both biopsies demonstrated PVD. We believe that the abnormalities seen on  $^{129}\text{Xe}$  MRI scans in these patients represent areas of PVD that are associated with a barrier to gas diffusion. Moreover, these changes appear to be different to those seen in other lung diseases associated with barriers to gas diffusion, such as idiopathic fibrosis. Among the objectives of this proposal is to clarify and strengthen these distinguishing features.

If successful,  $^{129}\text{Xe}$  MRI could overcome the current limitations of PVD diagnosis while conferring a number of potential benefits. First, imaging the abnormalities in the lungs allows the diagnosis of PVD in the setting of concomitant heart or lung disease. With HP  $^{129}\text{Xe}$  MRI, abnormalities in gas exchange secondary to PVD can be directly visualized. Second, non-invasive diagnosis of PVD could remove the need for an invasive RHC. While RHC is a relatively safe procedure, there are a number

of limitations to the interpretation of RHC, including arbitrary cutoffs for mPAP, PCWP, and PVR. Third, the abnormalities on HP Xe MRI could be used to non-invasively monitor response to therapy. If we are successful in demonstrating the applicability of HP Xe MRI, this technology holds the promise of greatly improving the diagnosis and management of PVD.

#### **4. Design & Procedures:**

This study seeks to deploy several forms of Xe MRI contrast as well as emerging conventional proton MRI techniques for imaging lung structure and perfusion. Specifically, the Xe MRI scans will provide 3D images of ventilation and gas exchange, and spectroscopic indices will be evaluated to test gas exchange dynamics with high temporal resolution. The conventional H MRI scans will include a free-breathing ultra-short echo time (UTE) scan that provides images similar to that of a CT scan. The overall aims of the study are as follows:

**Aim 1. Perform Xe MRI scans in cohorts of patients with PVD, isolated left sided heart failure and isolated lung disease:**

- 1.1 Deploy and optimize Xe gas exchange MR spectroscopy and imaging, Xe ventilation MRI, structural H UTE MRI, and breath-hold H perfusion MRI.
- 1.2 Conduct comprehensive H-Xe MRI in 10 patients with pure PAH
- 1.3 Conduct comprehensive MRI in 10 patients with pure left heart failure
- 1.4 Conduct comprehensive MRI in 10 patients with pure lung disease but no pulmonary hypertension
- 1.5 Conduct comprehensive MRI in 5 patients with Chronic thromboembolic pulmonary hypertension (CTEPH) pre and post PTE surgery.

**Aim 2. Develop diagnostic criteria for optimizing the sensitivity and specificity of Xe MRI for the diagnosis of PVD:**

- 2.1 Develop quantification/scoring methods based on PAH, left heart disease, and lung disease MRI
- 2.2 Develop reader training materials and train 3 expert readers
- 2.3 Begin prospective recruitment of 92 patients undergoing right heart catheterization for evaluation of PAH or other cardiac or pulmonary disease for MRI scans. These patients may be asked to return for a second scan in the study, at a time no earlier than 48hr after their last xenon dose.

**Aim 3. Perform a larger, single-blind study testing the diagnostic accuracy of Xe MRI for diagnosis of PVD:**

- 3.1 Trained readers will evaluate Xe MRI, while blinded to the subject's disease state and will determine the presence and severity of PVD
- 3.2 Diagnostic accuracy of Xe MRI will be compared to the gold standard of hemodynamic and clinical criteria of PAH
  - 3.2.1 The primary focus of Aim 3 is to compare Xe MRI capability to detect absence/presence of pre/post-capillary PH to the gold standard of RHC
    - a. For this PFTs are not necessary, so they are ancillary
    - b. However, they are a standard way to characterize patients for publications, etc, so we would like to get them if we can. Getting them from the medical record is perfectly adequate for this purpose.
      - i. If PFTs are not available from the medical record, they are not so critical as to prevent us from enrolling the subject. In publications we will simply acknowledge the realities of COVID for this missing data.

This will be a single-blinded, open-label study enrolling volunteers and patients with pure PAH (10 subjects), pure left heart disease (10 subjects), pure lung disease (10 subjects) and CTEPH (5 subjects) [Aim 1] followed by a larger cohort of 92 subjects who are undergoing right heart catheterization for evaluation of PAH or other cardiac or pulmonary disease. [Aim 2]. We plan to consent 127 subjects. No subject will be excluded from the study on the basis of gender or ethnicity. Female subjects of childbearing potential will undergo urine pregnancy testing before each MRI. The urine pregnancy test must be negative to continue participating in the study. To refine the precision of Xe MRI for imaging gas transfer efficiency,

we will acquire a hemoglobin level by finger sensor device for each subject testing at each study visit. Informed consent will be obtained before a subject begins any study intervention. Subjects will undergo an approximately hour long comprehensive MRI protocol

Patients with PAH, CTEPH, left heart disease and lung disease will be recruited using minimally restrictive inclusion/exclusion criteria. The Duke Center for Pulmonary Vascular Disease sees approximately 150 patients for evaluation of PAH including CTEPH in a year. For the first phase of the study, whether patients are receiving approved therapies, enrolled in clinical trials, or receiving no therapy, all will be eligible for inclusion in this MRI study. For the second phase of the study, patients who have PAH and receiving approved therapies, patients who are being evaluated for PVD or other cardiac or pulmonary disease will be included in the study.

Each study session will begin with a collection of relevant patient history and symptoms, measurement of hemoglobin levels, and urine pregnancy testing (if applicable) and finally pulmonary function testing. Pulmonary function testing will include one or more of spirometry, lung volumes and DLCO. Study team will use the PFTs that are available from the medical record. The subject will be escorted to the MRI suite where they will be fitted with a Xe transmit-receive vest coil. They will then be positioned supine on the scanner bed. They will be coached about how to inhale HP Xe from the dose delivery bags. Then the subject and bed will be moved into the scanner and they will undergo basic H localizer and anatomical scans. Once localization is complete, subjects will undergo several MRI scans after inhalation of HP Xe. Each dose will be limited to a volume less than 25% of subject lung capacity (TLC) as is the case for all protocols currently carried out under IND 109,490. After each Xe dose, the table will be moved out of the magnet bore and the subject queried for any symptoms. The next Xe dose and scan will be administered when the subject and study personnel are ready. Subjects will undergo a Xe MR spectroscopy calibration scan, Xe ventilation MRI, and Xe gas exchange MRI. Any given Xe MRI scan may be repeated, if necessary. There is no limit to the number of Xe scans allowed during the session, although current Xe production capabilities generally limit this to 5 Xe doses. After completing the Xe portion of the scan, the Xe coil will be removed and patients fitted with a torso array H coil. They will then undergo a free-breathing ultra-short-echo time H MRI to delineate lung structure. This completes the MRI exam, after which subjects will be free to go home or continue with their standard clinical care. Altogether, the procedures will take approximately 3-4 hours.

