## 12. Data Analysis & Statistical Considerations:

### Sample size

Our sample size calculation is based on testing whether the proposed diagnostic test based on Xe MRI has accuracy comparable to imaging diagnostic procedures in clinical practice, such as mammography. To this end, we propose to test the hypotheses H0: AUC = 0.72 vs. H1: AUC > 0.85, where AUC is a summary measure of diagnostic accuracy obtained as the area under the receiver operating characteristic (ROC) curve which displays the tradeoff between sensitivity and specificity for our proposed Xe MRI based diagnostic test. Here AUC = 0.72 represents a moderately accurate test while AUC = 0.85 represents accuracy comparable to clinical mammography. Based on a one sided, one sample test with variances approximated using the binormal model, we estimate a minimum sample size of 46 normals and 46 with disease will be required to test the above hypotheses at a significance level of 5% with 80% power.

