### Correlation

Our preliminary Xe MRI studies on patients with PAH, in combination with our previous experience with normals as well as those with other diseases, have helped us formulate quantitative metrics based on Xe MRI studies with high diagnostic potential for PAH. These metrics include the proportion of voxels with low RBC/Gas transfer and the amplitude of the wave seen in Xe MRI based spectroscopy. In Aim 2, our goal is to identify a combination of these metrics which optimally correlates with the current diagnostic standard for PAH which is based on measurements obtained from right heart catheterization, in a training set of 30 patients with and without the disease. The optimal combination will be obtained using discriminant analysis, in which the Xe MRI based metrics will be used as predictors and the diagnosis obtained from right heart catheterization as outcome. To identify the optimal combination and associated thresholds, we will consider all possible combinations of predictors, as well as a variety of discriminant analysis techniques, such as linear discriminant analysis and support vector machines. To avoid optimistic bias from overfitting, we will use leave out one cross validation to obtain an unbiased estimate of prediction error in the training set, which will be used to rank the most predictive discriminant rules. The actual diagnostic accuracy will be evaluated on a separate validation set of 92 patients in Aim 3.

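### The plan does not say which output enters the Aim 3 AUC test; if it is the presence-and-severity call or a thresholded class, power can fall below the stated 80%

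*Combined protocol and SAP*

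**What the plan says.** Section 12, Sample size, tests an AUC of 0.72 against 0.85 for the Xe MRI test. The method is described as "Based on a one sided, one sample test with variances approximated using the binormal model", and the result is that "a minimum sample size of 46 normals and 46 with disease will be required" "at a significance level of 5% with 80% power". The AUC comes from a ROC curve that trades sensitivity against specificity. The paragraph does not say what score generates the curve.

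Two outputs could feed it:

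- **Readers.** Section 4, Aim 3, item 3.1 has trained, blinded readers who "will determine the presence and severity of PVD". Item 3.2.1 gives the primary focus as the "capability to detect absence/presence of pre/post-capillary PH to the gold standard of RHC". No number of severity grades is given, and no rule for combining the three readers of item 2.2.
- **Discriminant rule.** Section 12, Correlation, combines quantitative Xe MRI metrics by discriminant analysis. The search over predictors and techniques is made "To identify the optimal combination and associated thresholds". Accuracy is then assessed in the same 92 validation patients.

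The plan does not state which output is tested against 0.72, or whether the AUC is empirical or fitted.

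**The concern.** A ROC area uses the ordering of all patients. A decision on presence, with a severity grade only for those judged positive, keeps the ordering above the presence cut and discards it below. Everyone read as absent shares one value, and the empirical ROC curve becomes a straight line beyond that point. A yes/no call leaves a single operating point, with area (sensitivity + specificity)/2. Analysing the thresholded class of the discriminant rule does the same.

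If the planning value of 0.85 belongs to the underlying continuous score, the area on the recorded scale is smaller and closer to 0.72, and the stated power no longer applies. For the readers, ordering that was never recorded among the absent reads cannot be recovered without re-reading the scans.

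**Working it through.** **Inputs from Section 12, Sample size.** Null AUC 0.72; alternative 0.85, taken as a point value; one-sided 5%; 80% power; 46 per group; binormal variance.

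**Reproducing the plan's figure.** With A = 1.414 × z(AUC) and 1:1 allocation, V = 0.0099 × exp(−A²/2) × [(5A² + 8) + (A² + 8)].

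- AUC 0.72: A = 0.824, V0 = 0.1415, SE at 46 per group = √(0.1415/46) = 0.0555.
- AUC 0.85: A = 1.466, V1 = 0.0977, SE = √(0.0977/46) = 0.0461.
- n = [(1.645 × √0.1415 + 0.842 × √0.0977)/0.13]² = 46.02 per group.
- Critical AUC = 0.72 + 1.645 × 0.0555 = 0.811. Power at 46 = Φ((0.85 − 0.811)/0.0461), about 80.0%.

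The 46 + 46 therefore reproduces.

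**Assumptions for the recorded scale.** The latent score is N(0, 1) in patients without disease and N(μ, 1) in those with disease, where μ = √2 × z(0.85) = 1.466, so the latent AUC is 0.85. The score is cut into ordered categories, and the empirical AUC (ties count one half) is tested one-sided against 0.72 with the DeLong SE. The documents give neither the cut positions nor the number of grades.

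**Yes/no at the best cut, by hand.** The cut is at μ/2 = 0.733, so sensitivity = specificity = Φ(0.733) = 0.768 and AUC = 0.768. SE = √[(0.768 × 0.232 + 0.768 × 0.232)/(4 × 46)] = 0.0440. Power ≈ Φ((0.768 − 0.72)/0.0440 − 1.645) = 0.29. Simulation gives 33% to 34%.

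**Absent plus three grades, by hand.** Cuts are at 0.733, 1.333 and 1.933.

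- Category probabilities without disease: 0.768, 0.141, 0.065, 0.027.
- With disease: 0.232, 0.215, 0.233, 0.320.
- AUC = 0.232 × 0.384 + 0.215 × 0.838 + 0.233 × 0.941 + 0.320 × 0.987 = 0.804.

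**Simulated power, 46 + 46, latent AUC 0.85.** Repeat runs differ by a point or two.

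| Output analysed | AUC on that scale | Power (DeLong) |
|---|---|---|
| Continuous score | 0.850 | 91% |
| Absent + 3 grades, presence-cut specificity 0.50 | about 0.82 | 77% to 79% |
| Absent + 3 grades, specificity 0.70 | about 0.82 | 71% |
| Absent + 3 grades, specificity 0.77 | 0.804 | 63% |
| Absent + 3 grades, specificity 0.84 | 0.78 | 42% |
| Yes/no, best cut | 0.768 | 34% |
| Yes/no, specificity 0.90 | 0.737 | 11% to 12% |

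The continuous score exceeds 80% because its empirical SE, about 0.040, is smaller than the 0.0461 of the planning formula.

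**Where the loss comes from.** Finer severity grading does not remove it. With very many grades above the presence cut, power is about 76%, 65% and 45% at specificity 0.70, 0.77 and 0.84.

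**When the loss is small or absent.**

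- Empirical AUC with the cuts placed to maximise it: 81% for four categories and 85% for five.
- Binormal AUC fitted to the ratings, spread cuts: 81% to 82% for four categories and 82% to 83% for five. With four categories and every cut at or above μ/2, it is 51% to 75%.
- 0.85 taken as the AUC on the recorded scale itself: 91% to 95% for two to five categories.

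**The case against.** A reader might infer that Aim 3 records only presence and severity and is therefore underpowered as written. The documents do not support that. Item 3.1 does not say that nothing else is recorded, and item 2.1 plans quantification and scoring methods before the readers are trained. The Correlation paragraph describes continuous metrics and a discriminant rule assessed in the same 92 patients; if its score is tested, 46 + 46 stands. Finding thresholds for a rule does not mean that its AUC is computed from the class, and a ROC curve implies a moving threshold. The Sample size paragraph never says that 0.85 belongs to a latent score, and its binormal model can also be fitted to ordinal ratings. All of this stands, and it makes the power loss conditional.

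The objection that four or five categories are enough stands only in part. The cuts giving 81% and 85% put the lowest boundary at specificity 0.47 and 0.39, so more than half of patients without disease would be read as having some PVD. That suits a likelihood scale but is hard to credit as a decision on presence. At lenient presence cuts the loss is modest: with three grades, power is 77% to 79% at specificity 0.50, and with ungraded severity above the cut it is 81% at 0.65. At specificity 0.70 or more, an empirical AUC stays below 80% however finely severity is graded.

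**Conclusion.** The concern holds in conditional form. The sample size is correctly computed, but the plan does not tie its AUC to a recorded output, and the one reader output it defines would tie all absent reads. If that call or a thresholded class is tested with an empirical AUC, and 0.85 is the AUC of the underlying continuous score, power is about 34% for yes/no at the best cut. It is about 71%, 63% and 42% for absent plus three grades at presence-cut specificity 0.70, 0.77 and 0.84. These figures rest on assumed cuts, an equal-variance binormal latent score and the DeLong test.

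It does not follow that a test with a true AUC of 0.85 would probably fail the plan's criterion. Several of the multi-grade scenarios have power above 50%, and three readings that the text allows lose little or nothing. The point merits correction because the choice is open, the lost ordering is hard to recover, and an output fixed in advance cannot be picked after the results are seen.

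**What to change.** 1. In Aim 3, item 3.1, have each reader record for every patient, before the presence and severity call, a graded likelihood that PVD is present (for example 0 to 100). Compute the reader AUC from that score. A stated ordinal likelihood scale would also serve: seven well-spread levels give an AUC of 0.843 and power of about 88% under the same assumptions.
2. In Section 12, state that any AUC for the discriminant rule uses its continuous score (posterior probability or decision value), not the thresholded class.
3. In the same place, name which of the two outputs is the primary test against 0.72, whether the AUC is empirical or fitted, and how the three readers are combined.

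The cost is one extra field on the reading form and one SAP sentence, or a little more if all of item 3 is spelled out. Recruitment, scanning and the 46 + 46 are unchanged.

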## 5. Selection of Subjects:

We propose to recruit and consent 10 subjects with known PAH, 10 subjects with isolated left heart disease, 10 subjects with isolated lung disease (either chronic obstructive pulmonary disease or interstitial lung disease) and 5 patients with CTEPH, followed by 92 subjects undergoing or having undergone an evaluation for PAH over the course of this research. These subjects will undergo an approximately hour long comprehensive MRI protocol, including hyperpolarized Xe administration. No subject will be excluded from the study on the basis of gender or ethnicity. Female subjects of childbearing potential will undergo pregnancy testing at study entry, and before each procedure. Informed consent will be obtained before a subject begins any study.

**Definition of PAH:** Mean PA pressure  $\geq$  25 mmHg with PCWP  $\leq$  15 mmHg and PVR  $\geq$  3 WU in the absence of significant left heart disease, lung disease, chronic pulmonary embolism, hemolytic anemia, sarcoidosis and cancer.

**Definition of isolated left heart disease:** Any of the following:

- 1) A mean PA pressure  $\geq$  25 mmHg with PCWP  $>$  15 mmHg and PVR  $<$  3 Woods units at right heart catheterization.
- 2) LVEF  $=<$  40% with mild or less RV enlargement and dysfunction on echocardiogram.

Evidence of diastolic dysfunction (as assessed by expert reader) with mild or less RV enlargement and dysfunction on echocardiogram.

**Definition of isolated lung disease:** A mean PA pressure  $<$  25 mmHg at right heart Cath AND/OR an estimated right ventricular systolic pressure of  $<$  40 on echocardiography AND/OR no diagnosis of heart

failure or pulmonary hypertension IN THE SETTING OF obstruction (FEV1/FVC < 0.7) on pulmonary function testing AND/OR radiographic evidence of lung disease.

**Definition of CTEPH:** Subjects with a history of a mean PA pressure  $\geq 25$  with evidence of chronic thromboembolic disease on imaging studies. Images may be obtained before and/or after pulmonary thrombendarterectomy (PTE) surgery for removal of blood clots from the lungs.

